Key Exclusion Criteria	
Any potential subject who meets any of the following criteria will be excluded from participating in the trial (applicable to both Dose Escalation and Expansion unless otherwise indicated)..
 
• Prior treatment with a CD37-targeting agent.• Prior allogeneic hematopoietic stem cell transplantation (HSCT).• Prior treatment with a CD3xCD20 bispecific antibody (GEN3009 + GEN3013 combination Expansion cohort only).• Autologous HSCT within 3 months before the first dose of GEN3009.• Lymphomas leukemic phase: high absolute lymphocyte count or the presence of abnormal cells in the peripheral blood indicating circulating lymphoma cells.• Treatment with an anti-cancer biologic including anti-CD20 therapy, radio-conjugated or toxin-conjugated antibody or chimeric antigen receptor T cell therapy within 4 weeks or 5 half-lives, whichever is shorter, before the first dose of GEN3009. Treatment with small molecules such as BTK inhibitors, BCL2 inhibitors, or PI3K inhibitors within 5 half-lives prior to the first dose of GEN3009.• Chemotherapy or radiation therapy within 2 weeks of the first dose of GEN3009.• Treatment with an investigational drug or an invasive investigational medical device within 4 weeks or 5 half-lives, whichever is shorter, prior to the first dose of GEN3009, and at any time during the study treatment period.• Autoimmune disease or other diseases that require permanent or high-dose immunosuppressive therapy.• Received a cumulative dose of corticosteroids more than the equivalent of 250 mg of prednisone within the 2-week period before the first dose of GEN3009.• Has uncontrolled intercurrent illness, including but not limited to:
a. Ongoing or active infection requiring intravenous antibiotics treatment at the time of enrollment or within the previous 2 weeks prior to the first dose of GEN3009 or GEN3013.b. Symptomatic congestive heart failure (grade III or IV as classified by the New York Heart Association ([NYHA])), unstable angina pectoris or cardiac arrhythmia (refer to Appendix 2) and/or known decrease ejection fraction of <45%c. Myocardial infarction, intracranial bleed, or stroke within the past 6 months.

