FDG-PET CT/CT/MRI ^c	9.2.2.1	X											
Lymphoma with Bone Marrow Involvement and CLL: Unilateral bone marrow biopsy and aspirate ^d	9.2.2.2	X											
Height	9.3.1	X											
Body Weight	9.3.1	X	X				X			X		X	
Physical Examination (including lymph node assessment) ^e	9.3.1	X	X				X			X		X	
Vital Signs	9.3.2	X	X ^f	X ^f	X	X ^f	X	X	X ^f	X		X ^f	X
ECG (in triplicate)	9.3.3	X	X ^g	X ^g	X	X ^g	X	X	X ^g			X ^g	
ECOG Performance Status	9.3.4	X	X										
Constitutional Symptoms	9.3.5	X	X			X			X			X	
Adverse Events ^h	10	X	X	X	X	X	X	X	X	X	X	X	X
Concomitant Medication and Procedures	9.1.4	X	X	X	X	X	X	X	X	X	X	X	X
Premedication prior to GEN3009 Administration	6.2		X	X ^j		X			X		X		
GEN3009 Administration	6.4.1		X	X ^j		X			X		X		

Treatment Cycle: 28-day cycle	Section	Screening	Cycle 1										
		≤ 21 days prior to C1D1	1d ^a	2d	4d	8d ^a	9d	11d	15d ^a	16d	18d	22d ^a	23d
Day					±1d	±1d		±1d	±1d		±1d		
LABORATORY ASSESSMENTS													
Hematology: Complete blood count and differential count ^e	9.4.1	X	X	X	X	X	X	X	X	X	X	X	X
Quantitative Lymphocyte Subsets	9.4.1	X											
Biochemistry ^e	9.4.1	X	X	X	X	X	X	X	X	X	X	X	X
Coagulation ^e	9.4.1	X	X	X	X	X	X	X	X	X	X	X	X
Immunoglobulins (IgA, IgE, IgG, IgM)	9.4.1	X											
Urinalysis ^e	9.4.1	X	X			X							
Serum β ₂ -microglobulin	9.4.1	X											
Pregnancy Test (serum)	9.4.1	X											
Pregnancy Test (either urine or serum) ^e	9.4.1		X										
HIV Serology ⁱ	9.4.1	X											
Hepatitis B and C Serology	9.4.1	X											
Cytomegalovirus (CMV) Serology	9.4.1	X											

- a. Subjects must remain at the clinic for at least 4 hours for observation following GEN3009 administration. Subjects must be instructed to contact the investigator should signs or symptoms of infusion-related reactions occur following discharge from the 4-hour observation period. Observation of up to 24 hours postdose during Cycle 1 is permissible at the discretion of the investigator.
- b. Any medical condition (ie, signs, symptoms and diagnosis) occurring prior to the first GEN3009 dose should be recorded as medical history.
- c. Refer to Section 9.2.2.1 for imaging requirements. Imaging assessments performed as SOC prior to the subject signing of informed consent may be submitted as screening assessment, if imaging is performed within 21 days of the first dose of GEN3009, and all other requirements for imaging are met.

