		Screening	1d	2d	2d+2h	4d	8d	15d	16d	22d
Day										
Visit window										
Tumor biopsy	9.7/9.8.2	X ^a						X ^{b,f}		
Cytokines	9.8.3.2		X ^c					X ^c		
Complement	9.8.3.3		X ^c	X ^{d,h}	X ^{d,i}			X ^c	X ^d	
Immunophenotyping	9.8.3.1		X ^c	X ^{d,h}		X ^{d,i}		X ^c	X ^d	
PBMC	9.8.3.1		X ^c				X ^{c,d}	X ^{c,d}		X ^{c,d}
Saliva DNA	9.8.3.4	X								
ctDNA/MRD plasma	9.8.3.4/9.2.2.3		X ^c					X ^{c,f}		

Treatment Cycle: 28-day cycle	Section	Cycle 3		Cycle 4-9		Cycle 10 and Beyond		Unscheduled	Treatment Discontinuation Visit
		1d	15d	1d	15d	1d			
Day			+2d	+3d	±3d	±4d			
Visit window									
Tumor biopsy	9.7/9.8.2								X ^b
Cytokine	9.8.3.2							X	
Complement	9.8.3.3			X ^e	X ^e	X ^e		X	X
Immunophenotyping	9.8.3.1	X ^c	X ^c	X ^{c,e}	X ^{c,e}	X ^{c,e}		X	
PBMC	9.8.3.1			X ^{c,e}				X	X
Saliva DNA	9.8.3.4								
ctDNA/MRD plasma	9.8.3.4/9.2.2.3	X ^c		X ^{c,g}		X ^{c,g}		X	

a. Fresh lymph node biopsy (to be taken from patients with easily accessible lesions) or an archival lymph node biopsy (formalin-fixed paraffin-embedded [FFPE], which is taken after most recent therapy prior to enrollment and taken within 6 months of Cycle 1 Day 1) is mandatory for lymphoma, SLL and CLL. Baseline biopsy samples are requested to be submitted by C1D1.

- b. Unless otherwise agreed with sponsor's medical monitor or delegate, a fresh core biopsy is to be taken from patients with easily accessible lesions in Cycle 2 (Week 6) and at the End of Treatment visit.
- c. If the visit occurs on an infusion day, the sample must be taken before IMP treatment (-30 minutes).
- d. Cycle 1 only.
- e. Samples in even cycles only, starting Cycle 4.
- f. Cycle 2 only.
- g. Samples to be taken C5, C7, C10 and C13 only. After C13 a sample will be obtained every 6 months (± 1 month) for up to 3 years.
- h. Only in case of full infusion on Day 1
- i. Only in case of split dose between Day 1 and Day 2

Table 9 Visit Assessment Schedule for MRD – Dose Escalation and Expansion GEN3009 Monotherapy

	Cycles 1, 2, 3, 5, 7, and 10	Cycle 13 and onward
Day or Time post dose (window)	Day 1 (+2 days)	Day 1 (+2 days)
Whole blood MRD ^a	X	A whole blood sample will be obtained every 6 months (\pm 1 month) for up to 3 years

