5.1.2 Expansion (including Safety Run-in) Inclusion Criteria

Each potential subject must fulfill all of the following criteria to be enrolled in the trial.

1. Be at least 18 years of age.
2. Must sign an ICF prior to any screening procedures indicating that they understand the purpose of the trial, the procedures required for the trial, and are willing to participate in the trial prior to any other trial-related assessments or procedures.
3. Has histologically or cytologically confirmed relapsed or refractory B-cell NHL. All subjects must have received at least 2 prior lines of systemic therapy, and,
 - a. For FL and DLBCL, at least 1 of the 2 prior lines of treatment must have been a CD20-containing systemic regimen;
 - b. For CLL, subjects must have received at least one prior line of BTK inhibitor or BCL-2 inhibitor.

Note: See Section 11.8.1.3 for definitions of “relapsed” disease.

4. Has 1 of the following B-cell NHL subtypes for the Expansion (including safety run-in):
 - a. DLBCL, de novo or histologically transformed
 - b. FL Grade 1, 2 and 3a, with advanced symptomatic disease and with a need for treatment initiation
 - c. CLL, must have active disease that needs treatment with at least 1 of the following criteria being met ([Hallek et al., 2018](#)):
 - i. Evidence of progressive marrow failure as manifested by the development of, or worsening of, anemia and/or thrombocytopenia
 - ii. Massive (ie, ≥ 6 cm below the left costal margin) or progressive or symptomatic splenomegaly
 - iii. Massive nodes (ie, ≥ 10 cm in longest diameter) or progressive or symptomatic lymphadenopathy
 - Progressive lymphocytosis with an increase of $\geq 50\%$ over a 2-month period, or LDT < 6 months
 - Autoimmune complications including anemia or thrombocytopenia poorly responsive to corticosteroids
 - Symptomatic or functional extranodal involvement (eg, skin, kidney, lung, spine)
 - Disease-related symptoms as defined by any of the following:
 - Unintentional weight loss $\geq 10\%$ within the previous 6 months

- Significant fatigue
- Fevers $\geq 38.0^{\circ}\text{C}$ (100.5°F) for 2 or more weeks without evidence of infection
- Night sweats for ≥ 1 month without evidence of infection

d. GEN3009 + GEN3013 combination cohort only: Documented CD20+ DLBCL or FL based on representative pathology report

5. Has measurable disease for B-cell NHL:

- a. A FDG-PET CT scan demonstrating positive lesion compatible with CT (or MRI)-defined anatomical tumor sites, and

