5.3 Screen Failures

Screen failures are defined as subjects who consent to participate in the clinical trial but do not meet the protocol-defined eligibility criteria (refer to Section 5.1 and 5.2). Minimal information to be documented includes demography, reason for screening failure (eg, eligibility criteria not met, subject withdrew consent, other reasons) and any SAEs or AEs related to a trial assessment.

Individuals who do not meet the criteria for participation in this trial (screen failures) may be rescreened. The rescreening must be approved by the sponsor to ensure that the safety of the subject is not compromised. Screen failures may be rescreened only once. Subjects are required to sign a new ICF if updates have been made since signing the most recent ICF. All eligibility criteria must be re-assessed at the rescreening visit.

Previously submitted tumor biopsy samples are acceptable if obtained within 6 months prior to Cycle 1 Day 1. The following screening assessments may be used for rescreening if performed ≤ 3 weeks prior to Cycle 1 Day 1 or if approved by sponsor:

- Previously submitted FDG-PET CT, CT, or MRI scans with acquisition date ≤ 3 weeks prior to Cycle 1 Day 1. Scans that exceed the 3-week window may be used for trial enrollment with sponsor's approval.
- Screening laboratory assessments with the protocol-defined timelines as indicated in the visit assessment schedules (refer to [Table 2](#) and [Table 5](#)).

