9.2.2.1 Radiographic Assessment

For B-cell NHL excluding CLL, an ¹⁸F-FDG-PET CT (or CT/MRI and FDG-PET when PET CT not available) must be performed at screening (ie, within 3 weeks prior to the first dose of GEN3009). For subjects with FDG-avid tumors at screening, all subsequent disease assessments will be performed with FDG-PET CT using the 5-point scale ([Barrington et al., 2014](#)). For subjects with non-avid or variably FDG-avid tumors, CT scan with IV contrast of neck/neck/abdomen/pelvis/additional known lesions will be performed. The CT component of the PET CT may be used in lieu of a standalone CT/MRI, only if the CT component is of similar diagnostic quality as a contrast enhanced CT performed without PET. If contrast enhanced PET CT is not available, a standalone diagnostic CT/MRI and a standard FDG-PET should be performed. If independent CT and PET scanners are used, and the subject is receiving both scans on the same day, the PET must be performed prior to the CT with IV contrast so as to not compromise PET results. The PET CT acquisition methodology (eg, administration of intravenous contrast) should remain consistent between screening and subsequent assessments for any given subject.

For CLL, CT/MRI must be performed at screening (ie, within 3 weeks prior to the first dose of GEN3009) and subsequent response assessments.

MRI may be used to evaluate sites of disease that cannot be adequately imaged using CT (in cases where MRI is desirable, the MRI must be obtained at screening and at all subsequent response evaluations). For all other sites of disease, MRI studies do not replace the required neck, chest, abdomen, and pelvic CT scans.

In monotherapy cohorts, an MRI or CT scan of the brain (with lumbar puncture) at screening and during the course of trial should be performed if clinically indicated. In the combination cohort with GEN3013, an MRI or CT scan of the brain is mandatory during screening within 21 days of C1D1, and lumbar puncture is required only if clinically indicated and required within 21 days of C1D1.

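### The response-baseline scan may be older than the last permitted chemotherapy or radiotherapy, so shrinkage from earlier treatment can be credited to GEN3009

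*Protocol*

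**What the plan says.** **Imaging.** For B-cell NHL and for CLL, Protocol Section 9.2.2.1 states that baseline imaging "must be performed at screening (ie, within 3 weeks prior to the first dose of GEN3009"; Table 29 repeats the 21-day limit. Footnote c of Tables 2, 5 and 10 accepts standard-of-care imaging done before consent "if imaging is performed within 21 days of the first dose of GEN3009, and all other requirements for imaging are met". For rescreened subjects, Section 5.3 adds: "Scans that exceed the 3-week window may be used for trial enrollment", subject to sponsor approval and with no stated upper limit.

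**Prior therapy.** The synopsis and Sections 5.2.1 and 5.2.2 exclude "Chemotherapy or radiation therapy within 2 weeks of the first dose of GEN3009" and "Treatment with small molecules such as BTK inhibitors, BCL2 inhibitors, or PI3K inhibitors within 5 half-lives prior to the first dose of GEN3009". Biologics and investigational drugs are excluded within 4 weeks or 5 half-lives, whichever is shorter.

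**Order of the two.** Neither document ties the scan to the end of prior therapy. An archival biopsy, by contrast, must be one "which is taken after most recent therapy prior to enrollment" (Table 8 footnote a; similarly Table 13, Section 9.7 and Table 32).

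**Analysis.** SAP Section 5.2.2 takes the last non-missing value before first dose as baseline. The ORR sensitivity analyses in SAP Section 10.1.1 vary only the assessor and the analysis set.

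**The concern.** The imaging window is wider than the chemotherapy and radiotherapy washout. A scan can therefore record the disease as it stood before the last prior treatment, while GEN3009 starts on the disease as it stood afterwards.

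ORR is the primary endpoint of the three monotherapy expansion cohorts, and CR rate is the primary endpoint of the combination DLBCL cohort. All are single-arm with about 20 subjects, so no control group shares the error.

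The two endpoints are affected differently:

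- **PR** is judged against baseline: at least a 50% fall in the summed products of diameters on CT (Appendix 7), reduced uptake on PET (Appendix 10), or at least a 50% nodal decrease in CLL (Appendix 8). Shrinkage between scan and Day 1 enters that comparison directly.
- **CR** is absolute: 5-point score 1 to 3 on PET, or target nodes of 1.5 cm or less on CT. The baseline scan matters here because it establishes measurable disease at entry. A subject largely cleared by earlier treatment after the scan could enter on an outdated picture and then be counted as a CR.

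**Working it through.** The plan states no figure for this point, and there is no hypothesis test, alpha or power to reproduce. The check is window arithmetic followed by exact intervals.

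**1. Chemotherapy and radiotherapy (documents only).** Scan limit 21 days; washout 14 days.

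- Span in which treatment may follow the scan = 21 − 14 = 7 days, from Day −21 to Day −14.
- Example: scan on Day −21, radiotherapy on Day −15, GEN3009 on Day 1. No exclusion criterion is broken.

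**2. Small molecules (half-life assumed).** Washout = 5 × t½. An overlap exists if 5 × t½ < 21 days, that is t½ < 4.2 days (100.8 h).

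| Assumed t½ | Washout, days | Overlap, days |
|---|---|---|
| 6 h | 1.25 | 19.75 |
| 24 h | 5 | 16 |
| 48 h | 10 | 11 |
| 72 h | 15 | 6 |
| 96 h | 20 | 1 |
| 120 h | 25 | 0 |

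This matters most in the CLL cohort, where Section 5.1.2 states: "For CLL, subjects must have received at least one prior line of BTK inhibitor or BCL-2 inhibitor". That line need not have been the most recent one.

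**3. Does anything close the gap?**

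- Footnote c requires all other imaging requirements to be met, but Section 9.2.2.1 sets none on order relative to therapy.
- Section 6.6.2 prohibits anti-lymphoma therapy during the trial. That does not reach the time between a pre-consent scan and consent.
- Irradiated lesions leave the response assessment only if radiotherapy is given during the trial (Sections 6.6.2 and 9.2.3.1).

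**4. Effect on a 20-subject rate.** One false responder = 1/20 = 5 points. Clopper-Pearson 95% intervals:

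| Responders | Rate | 95% CI |
|---|---|---|
| 2/20 | 10% | 1.2 to 31.7 |
| 3/20 | 15% | 3.2 to 37.9 |
| 4/20 | 20% | 5.7 to 43.7 |
| 6/20 | 30% | 11.9 to 54.3 |

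**5. Range of expected bias (assumed inputs).** Let f be the share of subjects treated after their baseline scan. Let q be the chance that such a subject is scored a responder because of that treatment alone. Expected bias = 100 × f × q points; P(at least one in 20) = 1 − (1 − fq)^20.

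| f | q | Bias, points | P(at least one) |
|---|---|---|---|
| 5% | 10% | 0.5 | 0.10 |
| 10% | 30% | 3.0 | 0.46 |
| 20% | 50% | 10.0 | 0.88 |

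The documents give neither f nor q, so these rows show a range and not an estimate.

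**The case against.** Several protections exist and deserve weight.

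- **Relapsed or refractory disease.** Section 11.8.1.3 requires prior failure, so a late response to a failed therapy is less likely. This stands, but bridging or palliative treatment shortly before entry is not excluded.
- **Prohibition during the trial.** SAP Section 5.8 starts trial participation at consent. On that reading the gap is mainly pre-consent standard-of-care scans. That narrows it without closing it, because footnote c expressly accepts such scans. Section 9.1.3 also contemplates washout of prior medication after consent.
- **Confounding conditions.** A general exclusion covers conditions that could confound assessments. It rests on investigator judgement and does not mention scan timing.
- **CLL.** A response must last 2 months (Section 11.8.1.2) and also draws on blood counts and marrow. This helps, but only in CLL/SLL.
- **Precision.** At 4/20 the interval is already 38 points wide (43.7 − 5.7) and nothing is tested. That is true, but a wide interval does not correct a shift in one direction.

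A reader might go further than the documents allow in three ways:

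- **Regrowth counted as progression.** One might infer that regrowth after stopping an inhibitor will be charged to GEN3009. Section 9.2.3.2 allows early nodal growth to be treated as pseudo-progression unless it continues or is confirmed by biopsy, so this half is weak.
- **Corticosteroids.** One might count the permitted 250 mg prednisone equivalent before first dose as a further source. It is small beside the mandatory premedication: prednisolone 100 mg before each of four Cycle 1 infusions in monotherapy (400 mg), and ten 100 mg doses in Cycle 1 of the combination (1,000 mg).
- **Rescreening scans.** The allowance beyond 3 weeks applies only to rescreened subjects, needs sponsor approval, and is worded as being for enrolment. It is a side route, not the main gap.

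**Conclusion.** The gap is real. For chemotherapy and radiotherapy it follows from the documents alone: 7 days in which treatment may follow the baseline scan with no exclusion criterion broken. For small molecules it depends on a half-life below 4.2 days, which is an assumption.

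The documents support saying that earlier treatment's effect can be credited to GEN3009. They do not support saying that it is or will be, because the number of subjects treated after their scan is unknown. Nor is CR rate a change from this scan; the route to a false CR is indirect. The firm size is 5 points per false responder in a cohort of 20. The 0.5 to 10 point range rests on assumed inputs. This is a weakness worth correcting because correction is cheap; it does not by itself undermine the cohorts.

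**What to change.** **Protocol.** In footnote c of Tables 2, 5 and 10, Section 9.2.2.1 and Section 5.3, require the scan used as response baseline to be acquired after the last dose or fraction of any prior anti-lymphoma therapy, as is already done for the archival biopsy. An earlier standard-of-care scan may support eligibility only.

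**SAP.** Section 9.1.5 of the protocol already collects dates of prior therapy. Use them to flag subjects whose baseline scan precedes their last therapy, report how many there are, and add an ORR/CR sensitivity analysis counting them as non-responders. The SAP is based on protocol version 4.0 and describes only the GEN3009 cohorts, so the CR analysis for the combination cohort must also go wherever that cohort's analysis is specified.

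**Cost and limits.** The cost is one sentence in each of these places, a derived flag, and a later or repeated screening scan in a few subjects. Washout periods and sample size do not change. The rule fixes the order of scan and therapy, not the interval between them: treatment on Day −15 and a scan on Day −14 would comply, and some later shrinkage could still come from that treatment. Carry-over is therefore reduced, not removed. Such subjects would not be caught by the flag either, so the interval from last therapy to baseline scan should be listed as well.

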1 VISIT ASSESSMENT SCHEDULES

The following visit assessments are provided in this section:

- Table 2 Visit Assessment Schedule for Screening and Cycle 1 - Dose Escalation
- Table 3 Visit Assessment Schedule from Cycle 2 and Beyond – Dose Escalation
- Table 4 Visit Assessment Schedule for PK, Immunogenicity, Biomarkers/Pharmacodynamics, and Tumor Lysis Syndrome Surveillance Sampling – Dose Escalation
- Table 5 Visit Assessment Schedule for Screening and Cycle 1 – Expansion GEN3009 Monotherapy
- Table 6 Visit Assessment Schedule from Cycle 2 and Beyond – Expansion GEN3009 Monotherapy
- Table 7 Visit Assessment Schedule for PK and ADA – Expansion GEN3009
- Table 8 Visit Assessment Schedule for Biomarkers – Expansion GEN3009 Monotherapy
- Table 9 Visit Assessment Schedule for MRD – Dose Escalation and Expansion GEN3009
- Table 10 Visit Assessment Schedule for Screening and Cycle 1 Expansion GEN3009 + GEN3013 (including Safety Run-in)
- Table 11 Visit Assessment Schedule from Cycle 2 and Beyond – Expansion GEN3009 + GEN3013
- Table 12 Visit Assessment Schedule for PK and ADA – Expansion GEN3009 + GEN3013 (including Safety Run-in)
- Table 13 Visit Assessment Schedule for Biomarkers – Expansion GEN3009 + GEN3013 (including Safety Run-in)
- Table 14 Visit Assessment Schedule for MRD – Expansion GEN3009 + GEN3013
- Table 15 GEN3013 Repriming Cycle – Expansion GEN3009 + GEN3013 (including Safety Run-in)

The assessment schedules list all the assessments and indicates with an “X” the visits when they are performed. In addition to the fixed visits, it may be necessary to perform some of the assessments at unscheduled time points if deemed clinically necessary by the investigator. All data obtained from these assessments must be supported in the subject’s source documentation.

Table 2 Visit Assessment Schedule for Screening and Cycle 1 - Dose Escalation

Treatment Cycle: 28-day cycle	Section	Screening	Cycle 1										
			≤ 21 days prior to C1D1	1d ^a	2d	4d	8d ^a	9d	11d	15d ^a	16d	18d	22d ^a
Day						±1d	±1d		±1d	±1d		±1d	
Visit Window						±1d		±1d		±1d		±1d	
Informed Consent	13.2.3	X (before any trial-specific procedures)											
Eligibility Criteria	5.1, 5.2	X											
Demographics	9.1.1	X											
Disease Status: Includes diagnosis and staging criteria	9.1.2	X											
Medical History ^b	9.1.3	X	X										
Prior Anti-neoplastic Therapy	9.1.5	X											
DLBCL or CLL Cytogenetics and Molecular Status	9.4.1	X											
FDG-PET CT/CT/MRI ^c	9.2.2.1	X											
Lymphoma with Bone Marrow Involvement and CLL: Unilateral bone marrow biopsy and aspirate ^d	9.2.2.2	X											
Height	9.3.1	X											
Body Weight	9.3.1	X	X				X			X		X	
Physical Examination (including lymph node assessment) ^e	9.3.1	X	X				X			X		X	
Vital Signs	9.3.2	X	X ^f	X ^f	X	X ^f	X	X	X ^f	X		X ^f	X
ECG (in triplicate)	9.3.3	X	X ^g	X ^g	X	X ^g	X	X	X ^g			X ^g	
ECOG Performance Status	9.3.4	X	X										
Constitutional Symptoms	9.3.5	X	X			X			X			X	
Adverse Events ^h	10	X	X	X	X	X	X	X	X	X	X	X	X
Concomitant Medication and Procedures	9.1.4	X	X	X	X	X	X	X	X	X	X	X	X
Premedication prior to GEN3009 Administration	6.2		X	X ^j		X			X		X		
GEN3009 Administration	6.4.1		X	X ^j		X			X		X		

Treatment Cycle: 28-day cycle	Section	Screening	Cycle 1										
		≤ 21 days prior to C1D1	1d ^a	2d	4d	8d ^a	9d	11d	15d ^a	16d	18d	22d ^a	23d
Day					±1d	±1d		±1d	±1d		±1d		
LABORATORY ASSESSMENTS													
Hematology: Complete blood count and differential count ^e	9.4.1	X	X	X	X	X	X	X	X	X	X	X	X
Quantitative Lymphocyte Subsets	9.4.1	X											
Biochemistry ^e	9.4.1	X	X	X	X	X	X	X	X	X	X	X	X
Coagulation ^e	9.4.1	X	X	X	X	X	X	X	X	X	X	X	X
Immunoglobulins (IgA, IgE, IgG, IgM)	9.4.1	X											
Urinalysis ^e	9.4.1	X	X			X							
Serum β ₂ -microglobulin	9.4.1	X											
Pregnancy Test (serum)	9.4.1	X											
Pregnancy Test (either urine or serum) ^e	9.4.1		X										
HIV Serology ⁱ	9.4.1	X											
Hepatitis B and C Serology	9.4.1	X											
Cytomegalovirus (CMV) Serology	9.4.1	X											

- a. Subjects must remain at the clinic for at least 4 hours for observation following GEN3009 administration. Subjects must be instructed to contact the investigator should signs or symptoms of infusion-related reactions occur following discharge from the 4-hour observation period. Observation of up to 24 hours postdose during Cycle 1 is permissible at the discretion of the investigator.
- b. Any medical condition (ie, signs, symptoms and diagnosis) occurring prior to the first GEN3009 dose should be recorded as medical history.
- c. Refer to Section 9.2.2.1 for imaging requirements. Imaging assessments performed as SOC prior to the subject signing of informed consent may be submitted as screening assessment, if imaging is performed within 21 days of the first dose of GEN3009, and all other requirements for imaging are met.
- d. CLL/SLL subjects and lymphoma subjects with bone marrow involvement: fresh bone marrow biopsy and aspirate are required. Prior bone marrow biopsy samples done within 4 weeks before Cycle 1 Day 1 are acceptable. Fresh bone marrow aspirate is mandatory at screening.
- e. Physical examination or clinical laboratory tests may be performed within 1 day prior to GEN3009 dosing
- f. On GEN3009 administration days in Cycle 1, vital signs are to be obtained: 1) Before administration, 2) 15 minutes (± 5 minutes) after administration and 3) every 30 minutes (± 5 minutes) during the 4-hour postdose observation period.
- g. In triplicate, 5 minutes apart (± 5 minutes), before GEN3009 administration and 1-2 hours (± 15 minutes) after administration.
- h. All AEs must be reported from the first GEN3009 dose until 30 days after the last dose (refer to Table 3 for details on the safety follow-up visit). Medical conditions that occur after the ICF is signed and prior to first GEN3009 dose should only be reported as AEs if they were assessed by the investigator to be caused by a protocol-mandated procedure (ie, tumor biopsy and/or CT scan), including washout or discontinuation of prior medications.
- i. HIV testing is required at screening only if required per local health authorities or institutional standards.

j. At dose levels \geq [REDACTED] mg, the first dose of GEN3009 can be split into 2 consecutive days (ie, [REDACTED] mg at C1D1 and remaining amount at C1D2) after approval of the sponsor's medical monitor.

Table 3 Visit Assessment Schedule from Cycle 2 and Beyond – Dose Escalation

Treatment Cycle: 28-day cycle		Cycle 2-3						Cycle 4-9		Cycle 10 and Beyond	Unscheduled	Treatment Discontinuati on Visit ^a	Safety Follow- up Visit ^a	Survival Follow- up ^b
Day	Section	1d	4d	8d	11d	15d	22d	1d	15d	1d	--	As soon as possible after withdrawn from treatment	30 days after last dose	Every 12 weeks after last dose
		±2d	±2d	±2d	±2d	±2d	±2d	±2d	±2d	±2d	±2d	+7d	+14d	±14d
Body Weight	9.3.1	X		X		X	X	X	X	X	X	X	X	
Physical Examination (including lymph node assessment) ^c	9.3.1	X						X		X	X	X	X	
Vital Signs	9.3.2	X ^d		X ^d		X ^d	X	X	X					
ECG (in triplicate)	9.3.3	X ^e		X ^e		X ^e	X	X	X					
ECOG Performance Status	9.3.4	X						X		X	X	X	X	
Constitutional Symptoms	9.3.5	X						X		X	X	X	X	
Adverse Events ^f	10	X	X	X	X	X	X	X	X	X	X	X	X	
Concomitant Medication and Procedures	9.1.4	X	X	X	X	X	X	X	X	X	X	X	X	
Premedication prior to GEN3009 Administration	6.2	X		X		X	X	X	X	X				
GEN3009 Administration	6.4.1	X		X		X	X	X	X	X				
New Anti-cancer Treatment											X	X	X	
Survival Status	9.3.6											X	X	X
EFFICACY ASSESSMENTS														
FDG-PET CT/CT/MRI	9.2.2.1	X ^g												

Treatment Cycle: 28-day cycle	Section	Cycle 2-3						Cycle 4-9		Cycle 10 and Beyond	Unscheduled	Treatment Discontinuation Visit ^a	Safety Follow-up Visit ^a	Survival Follow-up ^b
		1d	4d	8d	11d	15d	22d	1d	15d	1d	--	As soon as possible after withdrawn from treatment	30 days after last dose	Every 12 weeks after last dose
Day	Visit Window	±2d		±2d		±2d	±2d	±2d	±2d	±2d	±2d	+7d	+14d	±14d
Lymphoma with Bone Marrow Involvement and CLL: Unilateral bone marrow biopsy and aspirate	9.2.2.2	X (at time of CR and clinically indicated)												
LABORATORY ASSESSMENTS														
Hematology: Complete blood count and differential count ^c	9.4.1	X	X	X	X	X	X	X	X	X	X	X		
Biochemistry ^c	9.4.1	X	X	X	X	X	X	X	X	X	X	X		
Coagulation ^c	9.4.1	X	X	X	X	X	X	X	X	X	X	X		
Immunoglobulins (IgA, IgE, IgG, IgM)	9.4.1	X						X		X		X		
Urinalysis ^c	9.4.1	X						X		X	X	X		
Pregnancy Test (either urine or serum)	9.4.1	X						X		X	X	X	X	
Hepatitis B and C Serology	9.4.1										X ^h			

- a. Subjects discontinuing from treatment for any reason will have a safety follow-up visit 30 days after the last dose of GEN3009. If the subject initiates new anti-lymphoma therapy within 4 weeks of the last dose of GEN3009, the safety follow-up visit should be performed prior to starting new anti-cancer therapy.
- b. Subjects will enter the survival follow-up after completion of the safety follow-up or if new anti-cancer treatment has been started. Survival follow-up contact may be performed as a telephone call, email, or on-site visit.
- c. Physical examination and clinical laboratory tests may be performed within 1 day prior to GEN3009 dosing.
- d. On dosing days, vital signs are performed predose and postdose, and more frequently at the discretion of the investigator. If the subject has stable vital signs and no other issues, the subject may be discharged from the clinic after all assessments are completed as required by protocol. Subjects must be instructed to contact the investigator should signs or symptoms of infusion-related reactions occur following discharge from the clinic.
- e. In triplicate, 5 minutes apart (± 5 minutes), before GEN3009 administration and 1-2 hours (± 15 minutes) after administration.

- f. All AEs must be reported from the first GEN3009 dose until 30 days after the last dose. If the subject initiates new anti-lymphoma therapy within 30 days of the last dose of GEN3009, the safety follow-up visit should be performed prior to starting new anti-cancer therapy.
- g. Refer to Section [9.2.2.1](#) for imaging requirements.
- h. Only for subjects with positive serology.

Table 4 Visit Assessment Schedule for PK, Immunogenicity, Biomarkers/Pharmacodynamics, and Tumor Lysis Syndrome Surveillance Sampling – Dose Escalation

Treatment Cycle: 28-day cycle		Screening										Cycle 1 and 2									
Day	Visit window	≤ D21 prior to C1D1		1d	2d	4d	8d	9d	15d	16d	22d	23d	PK/ADA ^a /Cy/Co/I/TLS	PK ^g	PK/I/TLS	PK/ADA ^b /Cy/Co/I	PK/ADA ^b /I				
Predose (-30 minutes)	Fresh tumor biopsy or archival samples for IHC																				
End of infusion ^c (+5 minutes)			PK/Cy ^f /TLS		PK ^g /Cy ^g			PK/TLS			PK/Cy ^b		PK								
End of infusion +2 hours (± 15 minutes)			PK ^f /Cy ^f /TLS		PK ^g /Cy ^g			TLS			Cy ^b										
End of infusion +4 hours (± 30 minutes)			PK ^f /Cy ^f /Co ^f /I ^f /TLS		PK ^g /Cy ^g /Co ^g /I ^g			I ^b /TLS			Cy ^b /Co ^b /I ^b		I ^b								
End of infusion +24 hours (± 2 hours)					PK ^f /Cy ^f /I ^f /TLS				I ^b /TLS			I ^b				I ^b					
End of infusion +72 hours (± 24 hours) ^h							PK/I/TLS														

Treatment Cycle: 28-day cycle		Cycle 3				Cycle 4-9			Cycle 10 And Beyond		Unscheduled		Treatment Discontinuation Visit	
Day	Visit window	1d	8d	15d	22d	1d	15d	1d	1d	1d	1d	1d	1d	1d
Predose (-30 minutes)	PK/I/Co	PK/I/Co	PK/I/Co	PK/I/Co	PK/I/Co	PK/ADA ^d /I ^d /Co ^d	PK/I ^d /Co ^d	PK/ADA ^d /I ^d /Co ^d						
End of infusion ^c (+5 minutes)	PK	PK	PK	PK	PK	PK	PK	PK	PK	PK				
Unscheduled Visit											PK/ADA/I/Co/Cy/ TB ^e		PK/ADA	

Note: Sample collection timing may be modified during the trial based on emerging data.

PK=Pharmacokinetics (Section 9.5); ADA=anti-drug antibody (Section 9.6); Cy=cytokine (Section 9.8.3.2); Co=complement (Section 9.8.3.3);

I=immunophenotyping on peripheral blood (Section 9.8.3.1); TLS=tumor lysis syndrome (Table 31); TB=tumor biopsy (Section 9.7/9.8.2)

a. Day 1 ADA in Cycle 2 only.

b. Cycle 1 only.

c. After flush.

d. ADA and biomarker samples in even cycles only.

e. Refer to Section 9.7.

- f. Only in case of full dose on Day 1
- g. Only in case of split dose between Day 1 and Day 2.
- h. In case of split dose between Day 1 and Day 2, the Day 4 sample will be 48 hours after the complete infusion.

Table 5 Visit Assessment Schedule for Screening and Cycle 1 – Expansion GEN3009 Monotherapy

Treatment Cycle: 28-day cycle	Section	Screening	Cycle 1											
			≤21 days prior to C1D1	1d ^a	2d	4d	8d ^a	9d	11d	15d ^a	16d	18d	22d ^a	23d
Day														
Visit Window						±1d	±1d		±1d	±1d			±1d	
Informed Consent	13.2.3	X (before any trial-specific procedures)												
Eligibility Criteria	5.1, 5.2	X												
Demographics	9.1.1	X												
Disease Status: Includes diagnosis and staging criteria	9.1.2	X												
Medical History ^b	9.1.3	X	X											
Prior Anti-neoplastic Therapy	9.1.5	X												
DLBCL or CLL Molecular Status	9.4.1	X												
FDG-PET CT/CT/MRI ^c	9.2.2.1	X												
Lymphoma with Bone Marrow Involvement and CLL: Unilateral bone marrow biopsy and aspirate ^d	9.2.2.2	X												
Height	9.3.1	X												
Body Weight	9.3.1	X	X				X			X			X	
Physical Examination (including lymph node assessment) ^e	9.3.1	X	X				X			X			X	
Vital Signs	9.3.2	X	X ^f	X ^f	X	X ^f	X	X	X	X ^f	X		X ^f	X
ECG (in triplicate)	9.3.3	X	X ^g	X ^g	X	X ^g	X	X	X	X ^g			X ^g	
ECOG Performance Status	9.3.4	X	X											
Constitutional Symptoms	9.3.5	X	X				X			X			X	
Adverse Events ^h	10	X	X	X	X	X	X	X	X	X	X	X	X	X
Concomitant Medication and Procedures	9.1.4	X	X	X	X	X	X	X	X	X	X	X	X	X
Premedication prior to GEN3009 Administration	6.2			X	X		X			X			X	
GEN3009 Administration	6.4.1			X	X		X			X			X	
LABORATORY ASSESSMENTS														

Treatment Cycle: 28-day cycle	Section	Screening	Cycle 1											
			≤ 21 days prior to C1D1	1d ^a	2d	4d	8d ^a	9d	11d	15d ^a	16d	18d	22d ^a	23d
Day														
Visit Window						$\pm 1d$	$\pm 1d$		$\pm 1d$	$\pm 1d$			$\pm 1d$	
Hematology: Complete blood count and differential count ^e	9.4.1	X	X	X	X	X	X	X	X	X	X	X	X	X
Quantitative Lymphocyte Subsets	9.4.1	X												
Biochemistry ^e	9.4.1	X	X	X	X	X	X	X	X	X	X	X	X	X
Coagulation ^e	9.4.1	X	X	X	X	X	X	X	X	X	X	X	X	X
Tumor Lysis Syndrome Panel	9.4.1			X	X	X	X	X	X	X	X	X	X	X
Immunoglobulins (IgA, IgE, IgG, IgM)	9.4.1	X												
Urinalysis ^e	9.4.1	X	X				X							
Serum β_2 -microglobulin	9.4.1	X												
Pregnancy Test (serum)	9.4.1	X												
Pregnancy Test (either urine or serum) ^e	9.4.1			X										
HIV Serology ⁱ	9.4.1	X												
Hepatitis B and C Serology	9.4.1	X												
Cytomegalovirus (CMV) Serology	9.4.1	X												

- a. Subjects must remain at the clinic for at least 2 hours for observation following GEN3009 administration. Subjects must be instructed to contact the investigator should signs or symptoms of infusion-related reactions occur following discharge from the 2-hour observation period.
- b. Any medical condition (ie, signs, symptoms and diagnosis) occurring prior to the first GEN3009 dose should be recorded as medical history.
- c. Refer to Section 9.2.1 for imaging requirements. Imaging assessments performed as SOC prior to the subject signing of informed consent may be submitted as screening assessment, if imaging is performed within 21 days of the first dose of GEN3009, and all other requirements for imaging are met.
- d. CLL/SLL subjects and lymphoma subjects with bone marrow involvement: fresh bone marrow biopsy and aspirate are required. Prior bone marrow biopsy samples done within 4 weeks) before Cycle 1 Day 1 are acceptable. Fresh bone marrow aspirate is mandatory at screening.
- e. Physical examination and clinical laboratory tests may be performed within 1 day prior to GEN3009 dosing.
- f. On GEN3009 administration days in Cycle 1, vital signs are to be obtained: 1) Before administration, 2) 15 minutes (\pm 5 minutes) after administration and 3) every 30 minutes (\pm 5 minutes) during the 2-hour postdose observation period.
- g. In triplicate, 5 minutes (\pm 5 minutes) apart, before GEN3009 administration and 1-2 hours (\pm 15 minutes) after administration.
- h. All AEs must be reported from the first GEN3009 dose until 30 days after the last dose. Medical conditions that occur after the ICF is signed and prior to first GEN3009 dose should only be reported as AEs if they were assessed by the investigator to be caused by a protocol-mandated procedure (ie, tumor biopsy and/or CT scan), including washout or discontinuation of prior medications.
- i. HIV testing is required at screening only if required per local health authorities or institutional standards.
- j. At dose levels \geq CCI mg, the first dose of GEN3009 can be split into 2 consecutive days (ie, CCI mg at C1D1 and remaining amount at C1D2) after approval of the sponsor's medical monitor.

Table 6 Visit Assessment Schedule from Cycle 2 and Beyond – Expansion GEN3009 Monotherapy

Treatment Cycle: 28-day cycle	Section	Cycle 2-3						Cycle 4-9		Cycle 10 And Beyond	Unscheduled	Treatment Discontinuation Visit ^a	Safety Follow-up Visit ^a	Survival Follow-up Visit ^b
